7.8. Treatment after the End of the Study

7.8.1. Special Treatment Considerations (Rescue Therapy)

Investigators will be trained on how to apply decision criteria for the timing and method of intervention in patients who do not reach glycemic targets during the 26-week treatment period. An additional therapeutic intervention should be considered in patients who meet the following criteria:

• The patients are fully compliant with assigned therapeutic regimen.

AND

- In the absence of any acute condition that raises blood glucose either of the following occurs:
 - Ouring the first 6 weeks post-randomization: An average fasting glucose level above 270 mg/dL (15.0 mmol/L) occurs over at least a 2-week period (at least 4 values/week must be available).

OR

O Any time after the first 6 weeks to 26 weeks post-randomization: An average fasting glucose level above 240 mg/dL (13.3 mmol/L) occurs over at least a 2-week period (at least 4 values/week must be available).

If these conditions are met, then patients may begin treatment with another antihyperglycemic agent as determined by their physician. If treatment with another antihyperglycemic agent is instituted, then study drug should be permanently discontinued. Patients may remain in the study for safety follow-up, but the date at which they begin rescue therapy will be the last date for collection of efficacy measures.

8. Discontinuation Criteria

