- If the patient intentionally misses 4 or more doses (consecutive or not) of study medication or intentionally or repeatedly takes more than the prescribed dose of study medication (see Section 9.3).
- If the patient develops any exclusion criteria, such as pregnancy or nursing.

If study drug is permanently discontinued, the patient should remain in the study if possible.

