8.1.2. Temporary Discontinuation from Study Treatment

After randomization, the investigator may temporarily discontinue study drug, for example, due to an AE (e.g., nausea and vomiting), a clinically significant laboratory value, or a natural disaster. If study drug discontinuation is due to an AE, the event is to be followed and documented. Every effort should be made by the investigator to maintain patients in the study and to restart study drug promptly after any temporary discontinuation, as soon as it is safe to do so. The dates of study drug discontinuation and restart will be documented. Patient noncompliance should not be recorded as temporary discontinuation of study drug on the eCRF.

In the event that the patient requires the discontinuation of the study drug, he/she may continue participation in the study, attend all visits, and undergo all protocol procedures, and patient data from the time of discontinuation of study drug will not be included in the primary analyses.

After study drug discontinuation, patients may commence any standard diabetes therapy in line with local or regional standards of care, and as considered appropriate by the investigator.

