10.3. Statistical Analyses

10.3.1. General Statistical Considerations

Statistical analysis of this study will be the responsibility of Lilly or its designee. Any change to the statistical methods described in the protocol will require an amendment only if it changes a principal feature of the protocol. Any other change to the statistical analyses and the justification for the change will be described in the statistical analysis plan (SAP) and/or clinical study report. Additional exploratory analyses of the data may be performed as deemed appropriate. Analyses will be fully detailed in the SAP.

The intention-to-treat (ITT) population is defined as all randomized patients. Statistical analyses (including the primary analysis) will be conducted on the modified ITT (mITT) population. The mITT population is defined as all randomized patients with at least 1 post-baseline measurement according to the treatment the patients were assigned. The per-protocol (PP) population is defined as all randomized patients who were compliant with study drug and completed the protocol and is a subset of the mITT population. The safety population is defined as all randomized patients who have received at least 1 dose of study drug. Safety analyses will be performed on the safety population.

Some efficacy measures will also be analyzed on the PP dataset. The PP analysis will include patients who meet the following additional criteria:

- Have been appropriately randomized
- Have not discontinued from the study for any of the early discontinuation criteria
- Have not missed 4 or more doses during the treatment period
- Have not been rescued or taken a concomitant antihyperglycemic medication besides metformin for more than 7 cumulative days during the treatment period

Patients who have had rescue therapy will be included in the mITT population, but not the PP population. The efficacy measures will be censored at the time of rescue for analyses using mITT population.

No adjustments for multiplicity will be performed.

All tests of treatment effects will be conducted at a one-sided alpha level of 0.1 and/or one-sided 90% confidence interval, unless otherwise stated.

The baseline value used for the analyses will be the last scheduled baseline value obtained for each patient prior to randomization.

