10.3.6.3. Exploratory Analyses

The change from baseline of 7-point SMBG profiles will be calculated using a similar MMRM-based model to the one used for the primary analysis. The corresponding baseline will be used in the model instead of the baseline HbA1c levels. The MMRM model will also include a term for the HbA1c stratification group.

Statistical analyses on categorical exploratory objectives like the effect of intrinsic factors, such as baseline levels of endogenous FGF-21, GLP-1, or GIP, on the pharmacologic effects of LY3298176 will be done using a logistic regression analysis with fixed effects of treatment, metformin use, and HbA1c strata.

Genetic markers will be evaluated for their contribution to the variability of LY3298176 pharmacology and will also be included as covariates in PK/PD model-based analyses if applicable.

LY3298176 concentration—response analyses of exploratory biomarkers may be performed.

Exploratory analysis on efficacy endpoints such as HbA1c and body weight may be performed on dataset that includes data from patients who received rescue therapy.

Other exploratory subgroup analyses may be performed as deemed appropriate.

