6.9.1.3. Supporting Analyses of Primary Outcome

The following supportive analyses will be performed for the primary outcome:

- An analysis using the same statistical model as the primary analysis will also be performed using mITT population on treatment without rescue dataset.
- The change in HbA1c from baseline will be analyzed using MMRM with restricted maximum likelihood estimation described in section 6.1.1. Comparisons between each LY3298176 dose arm with dulaglutide and placebo will be made. This analysis will be performed on three analyses sets: mITT population on treatment without rescue data, mITT population with all data, and PP dataset.
- An ANCOVA model will be used on the last observation carried forward (LOCF) endpoint of HbA1c as described in section 6.1.2. using MITT on treatment without rescue, and mITT population.

Table 6.3 describes the analyses to meet the primary objective, all performed on the HbA1c change from baseline values, including the above sensitivity analyses.

Analysis Type	LOCF or Observed Values	Analysis Set
Hierarchical Logistica	Observed	mITT without
		rescue
Hierarchical Logistic	Observed	mITT on treatment
		without rescue
MMRM	Observed	mITT
MMRM	Observed	PP
MMRM	Observed	mITT on treatment
		without rescue
MMRM, subgroup analyses	Observed	mITT on treatment
		without rescue
ANCOVA	LOCF	mITT on treatment
		without rescue,
		mITT

Table 6.3. Summary of Analyses for Primary Outcome

Abbreviations: ANCOVA = analysis of covariance; HbA1c = hemoglobin A1c; LOCF = last observation carried forward; mITT = modified intent-to-treat; MMRM = mixed model repeated measures; PP = per protocol.

a primary analysis

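### Protocol 7.8.1 ends efficacy collection at rescue while other sections allow for post-rescue efficacy data, so what the SAP's all-data HbA1c and weight analyses contain is unsettled

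*Protocol*

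**What the plan says.** **On collection.** Protocol 7.8.1 ties rescue to stopping study drug: "If treatment with another antihyperglycemic agent is instituted, then study drug should be permanently discontinued". The patient may stay for safety follow-up, but "the date at which they begin rescue therapy will be the last date for collection of efficacy measures". Protocol 8.1.1 says: "If study drug is permanently discontinued, the patient should remain in the study if possible". Protocol 8.1.2 says of a patient who has to stop study drug that "he/she may continue participation in the study, attend all visits, and undergo all protocol procedures", and adds: "After study drug discontinuation, patients may commence any standard diabetes therapy in line with local or regional standards of care". Section 8.1.2 is headed as temporary discontinuation, but it makes no exception for rescued patients. Nor does the Schedule of Activities.

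**On analysis.** Protocol 10.3.1 states: "The efficacy measures will be censored at the time of rescue for analyses using mITT population". Protocol 10.3.6.3 nevertheless foresees that exploratory analyses of endpoints such as HbA1c and body weight "may be performed on dataset that includes data from patients who received rescue therapy". SAP 6.9 removes post-rescue data from the primary analysis. From most other efficacy analyses it also removes data after study drug is stopped. It then adds analyses of HbA1c and weight on everything available in the mITT population. In SAP 6.9.1.3 the MMRM is run on the on-treatment, rescue-censored set, on the "mITT population with all data, and PP dataset". The LOCF ANCOVA is run on the on-treatment set and on the full mITT population.

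**On weight.** Protocol 10.3.4.1 lists body weight among the safety measures, and SAP 6.10 keeps post-rescue values in the safety analyses.

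Neither document gives an expected rescue rate, and the SAP states no estimand for the all-data analyses.

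**The concern.** The sentence in 7.8.1 governs what is measured, not only what is analysed. A value that was never collected cannot be restored by choosing a wider analysis set. The SAP distinguishes sets with and without post-rescue data, and that distinction has content only if such data exist.

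At stake is the reading of the all-data result. If it agrees with the rescue-censored result, a reader may conclude that rescue made no difference. Under 7.8.1 the two would agree on HbA1c in rescued patients because they use the same records. Rescue may also be uneven across arms: the sample-size table assumes no HbA1c change on placebo, and screening HbA1c may be as high as 10.5%. The protocol itself plans to compare rescue between arms by logistic regression and a log-rank test (10.3.3.3.2).

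**Working it through.** **Step 1. What each set holds under each reading.**

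| Records | On-treatment set | Without-rescue set (primary) | All-data set if 7.8.1 is followed | All-data set if sites follow 8.1.2 |
|---|---|---|---|---|
| On drug, before any rescue | in | in | in | in |
| Off drug, never rescued | out | in | in | in |
| HbA1c after rescue | out | out | none collected | in, where measured |
| Weight after rescue | out | out | possibly, if taken for safety | in, where measured |

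Under 7.8.1 the all-data set therefore has the same HbA1c records as the primary set. Against the on-treatment set it adds only off-drug values in unrescued patients. For a rescued patient, LOCF carries the same pre-rescue HbA1c forward in both ANCOVA sets. Under 8.1.2 the content depends on local practice.

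**Step 2. Whether another planned analysis covers the gap.** SAP 6.9.2.3 imputes missing HbA1c and weight from observed placebo data. It needs no post-rescue values. For LY3298176 patients it is a real check against data missing not at random. For a rescued placebo patient it borrows from placebo patients with observed values, who under 7.8.1 are the unrescued ones, so it is weak there.

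**Step 3. Scale.** Inputs from Protocol 10.1: 300 patients in 6 equal arms, 10% dropout, SD 1.0.
- Per arm: 300 / 6 = 50 randomized; 50 × 0.9 = 45 completers, as the plan states.
- Standard error of a two-arm contrast: 1.0 × √(2/45) = 0.211.

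As background, a normal approximation with known SD and a shared placebo arm gives 98.3% at 45 per arm for at least one dose beating the −0.8 bound, against the plan's approximate 98%. This point does not change that figure.

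**Step 4. Illustration.** The rescue rate r and the shift g are assumptions. Here g is the week-26 HbA1c actually reached after rescue minus the value modelled without rescue. Shift in arm mean = r × g.

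| r (patients of 50) | g = −0.5 | g = −1.0 | g = −1.5 |
|---|---|---|---|
| 2% (1) | −0.01 | −0.02 | −0.03 |
| 5% (2.5) | −0.025 | −0.05 | −0.075 |
| 10% (5) | −0.05 | −0.10 | −0.15 |
| 20% (10) | −0.10 | −0.20 | −0.30 |

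In standard errors of the contrast the range runs from 0.01 / 0.211 = 0.05 to 0.30 / 0.211 = 1.4. If only placebo patients were rescued, the assumed 15 mg contrast of −1.44 would become −1.43 to −1.14 in an analysis that included post-rescue values. Rescue in the LY3298176 arm would offset part of this. An all-data set without post-rescue HbA1c would miss the shift.

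**The case against.** Much of the case on the other side stands.

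- A reader might infer that the all-data analyses certainly contain no post-rescue values. The documents do not settle this. Sections 8.1.1, 8.1.2 and 10.3.6.3 and the wording of SAP 6.9 allow for such data, and weight may well be collected for safety.
- A reader might infer that the all-data analysis was meant as a treatment-policy check. The SAP calls these analyses supportive and gives them no such purpose.
- A reader might infer that the primary missing-data assumption is left wholly untested. It is not: placebo-based imputation and LOCF ANCOVA are planned. Values observed on another glucose-lowering agent would also answer a different question. They show outcome regardless of rescue, and would differ from the modelled unrescued outcome even if that model were right.
- The all-data set is not empty of added information. Compared with the on-treatment set, it keeps off-drug values in unrescued patients.
- The upper end of the illustration is generous. Ten rescued patients in one arm would be twice the 5 non-completers per arm implied by 10% dropout, and rescue requires sustained high fasting glucose.

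None of this removes the conflict between 7.8.1 and the other sections, or tells an analyst what the all-data set will hold.

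**Conclusion.** The inconsistency is real and should be resolved. Followed as written, 7.8.1 leaves the all-data MMRM and LOCF ANCOVA without post-rescue HbA1c, so they cannot show the treatment difference regardless of rescue. If 8.1.2 is followed instead, they will rest on incomplete post-rescue data. HbA1c is the clear gap; weight is less certain.

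The size cannot be derived from the documents. The range of about 0.01 to 0.30 HbA1c points rests entirely on the assumed rescue rates (2% to 20%) and shifts (0.5 to 1.5 points), and at low rescue rates it is negligible. The primary analysis, which censors at rescue by design, and the sample-size figures are unaffected. This is a worthwhile, inexpensive improvement, not a flaw in the primary result.

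**What to change.** **Protocol.** Reconcile 7.8.1 with 8.1.2 and 10.3.6.3. Amend only the collection sentence in 7.8.1, so that scheduled HbA1c, weight and other efficacy measures continue after rescue in patients who remain in the study, with each value flagged as post-rescue. Keep the primary set censored at rescue.

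**SAP.** Define the all-data set, state the question that its analyses answer, and report the number of post-rescue HbA1c and weight values per arm. If collection does stop at rescue, relabel the all-data analyses as adding only off-drug data from unrescued patients.

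**Cost.** HbA1c is already scheduled at every treatment visit that is not PK-specific, so the addition is a small assay and data-handling cost in rescued patients who stay. Because 7.8.1 says only that they may stay, some post-rescue values will still be missing; the counts per arm would show how many. No change to the rescue criteria or to treatment is proposed.

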8.1. Discontinuation from Study Treatment

8.1.1. Permanent Discontinuation from Study Treatment

Discontinuation of the investigational product for abnormal liver tests **should be considered** by the investigator when a patient meets one of the following conditions after consultation with the Lilly-designated medical monitor:

- Abnormal liver tests or when a patient meets one of the following conditions:
 - o ALT or aspartate aminotransferase (AST) >8× ULN
 - o ALT or AST >5× ULN for more than 2 weeks
 - ALT or AST >3× ULN and total bilirubin level >2× ULN or prothrombin time >1.5× ULN
 - o ALT or AST >3× ULN with the appearance of fatigue, nausea, vomiting, right upper-quadrant pain or tenderness, fever, rash, and/or eosinophilia (>5%)
 - o Alkaline phosphatase (ALP) >3× ULN
 - \circ ALP >2.5× ULN and total bilirubin >2x ULN
 - o ALP >2.5× ULN with the appearance of fatigue, nausea, vomiting, right quadrant pain or tenderness, fever, rash, and/or eosinophilia (>5%)
- Investigator Decision
 - the investigator decides that the patient should be discontinued from the study medication
- Any medication for weight loss is given for more than 1 week
- Adverse Event
- When any one of the following events occur, Lilly or its designee is to be alerted immediately:
 - o Pancreatitis or pancreatic cancer (refer to Section 9.2.1.2.5 for details)
 - o Estimated glomerular filtration <30 mL/min
 - Any severe injection site reaction or 2 or more moderate injection site reactions occurring a week or more apart
 - o Any significant study drug-related hypersensitivity reaction
 - Any nonfatal major cardiovascular (CV) events (refer to Section 9.2.1.2.6 for details)
 - Any other treatment-emergent adverse event (TEAE), SAE, or clinically significant laboratory value for which the investigator believes that permanent study drug discontinuation is the appropriate measure to be taken.
- If the patient, for any reason (including protocol-mandated institution of rescue therapy; see Section 7.8.1), requires treatment for greater than 1 week with another therapeutic agent that has been demonstrated to be effective for treatment of diabetes. Also, a change in dose of metformin is not allowed (except for incidences of hypoglycemia; see Section 7.1). However, a change to an equivalent dose strength from immediate-release to extended-release (or vice versa) formulation is allowed.

- If the patient intentionally misses 4 or more doses (consecutive or not) of study medication or intentionally or repeatedly takes more than the prescribed dose of study medication (see Section 9.3).
- If the patient develops any exclusion criteria, such as pregnancy or nursing.

If study drug is permanently discontinued, the patient should remain in the study if possible.

8.1.2. Temporary Discontinuation from Study Treatment

After randomization, the investigator may temporarily discontinue study drug, for example, due to an AE (e.g., nausea and vomiting), a clinically significant laboratory value, or a natural disaster. If study drug discontinuation is due to an AE, the event is to be followed and documented. Every effort should be made by the investigator to maintain patients in the study and to restart study drug promptly after any temporary discontinuation, as soon as it is safe to do so. The dates of study drug discontinuation and restart will be documented. Patient noncompliance should not be recorded as temporary discontinuation of study drug on the eCRF.

In the event that the patient requires the discontinuation of the study drug, he/she may continue participation in the study, attend all visits, and undergo all protocol procedures, and patient data from the time of discontinuation of study drug will not be included in the primary analyses.

After study drug discontinuation, patients may commence any standard diabetes therapy in line with local or regional standards of care, and as considered appropriate by the investigator.

8.1.3. Discontinuation of Inadvertently Enrolled Patients

The criteria for enrollment must be followed explicitly. If the sponsor or investigator identifies a patient who did not meet enrollment criteria and was inadvertently enrolled, notified discussion must occur between the sponsor CRP/clinical research scientist (CRS) and the investigator to determine if the patient may continue in the study. If both agree that it is medically appropriate to continue, the investigator must obtain documented approval from the sponsor CRP/CRS to allow the inadvertently enrolled patient to continue in the study with or without treatment with the investigational product.

8.2. Discontinuation from the Study

Some possible reasons that may lead to permanent discontinuation include the following:

- Enrollment in any other clinical trial involving an investigational product or enrollment in any other type of medical research judged not to be scientifically or medically compatible with this study
- Sponsor decision
 - Participation in the study needs to be stopped for medical, safety, regulatory, or other reasons consistent with applicable laws, regulations, and Good Clinical Practice (GCP).

- Investigator decision
 - o The investigator decides that the patient should be discontinued from the study
- Subject decision
 - The patient requests to be withdrawn from the study.

Patients who discontinue the study early will have end-of-study procedures performed as shown in the Schedule of Activities (Section 2).

8.3. Lost to Follow-Up

A patient will be considered lost to follow-up if he/she repeatedly fails to return for scheduled visits and is unable to be contacted by the study site. Site personnel are expected to make diligent attempts to contact patients who fail to return for a scheduled visit or were otherwise unable to be followed up by the site.

Site personnel, or an independent third party, will attempt to collect the vital status of the patient within legal and ethical boundaries for all patients randomized, including those who did not get investigational product. Public sources may be searched for vital status information. If vital status is determined, this will be documented and the patient will not be considered lost to follow-up.

Lilly personnel will not be involved in any attempts to collect vital status information.

9. Study Assessments and Procedures

Section 2 lists the Schedule of Activities, with the study procedures and their timing (including tolerance limits for timing).

Appendix 2 lists the laboratory tests that will be performed for this study.

Unless otherwise stated in the subsections below, all samples collected for specified laboratory tests will be destroyed within 60 days of receipt of confirmed test results. Certain samples may be retained for a longer period, if necessary, to comply with applicable laws, regulations, or laboratory certification standards.

9.1. Efficacy Assessments

9.1.1. Primary Efficacy Assessments

The primary efficacy measure is HbA1c, as determined by the central laboratory. Blood samples for HbA1c measurements will be collected at specific clinic visits as summarized in Section 2.

